STUDY PROTOCOL

Official Title: Daily Personalized Drinking Feedback Delivered Via Mobile Phone

Brief Title: Alcohol Feedback, Reflection and Morning Evaluation

NCT number: NCT05509218

Document date: March 27, 2026

(1) Baseline assessment and orientation. An onboarding session (~60 minutes), conducted via Zoom, involved providing informed consent, completing a brief baseline questionnaire and further orientation to study procedures. Data needed to personalize the intervention content were collected during the baseline survey. Participants were asked to choose from a range of possible goal types (e.g., max drinks per drinking event, drinks per week, weekly frequency of drinking, “skip goals”, “delay goals”, slow goals”, “stop goals”), as well as goals for calories and spending on alcohol. To assist this process, they were provided with NIAAA guidelines for safe drinking ($\leq 3/4$ drinks/day and $\leq 7/14$ drinks/week for women/men) and a reminder of their self-reported drinking patterns. They viewed a list of negative drinking consequences and checked off any they saw as important to avoid over the next month. Then they viewed a list of protective behavioral strategies (PBS) and indicated which PBS they had found useful in the past. Each of these data points was designed to be integrated/contrasted with subsequent self-reported behavior on morning reports during the intervention period. After the baseline survey, a research assistant reviewed study procedures. Participants were trained in standard drink definitions (12 oz beer, 5 oz wine, 1.5 oz liquor) and in the completion of mobile surveys and feedback report viewing. Participants practiced completing a morning report.

(2) Randomization. Randomization occurred following consent. However, participants were not informed of their group until they completed the baseline survey. The pilot RCT included three conditions (mobile personalized feedback intervention (PFI) with daily incentive for surveys, mobile PFI without daily incentives, assessment-only). After consent, participants were assigned using a random number table to one of these three conditions ranging in possible compensation from \$110 (assessment only, or PFI without incentives) to \$138 (full compliance in PFI with daily incentives). Using their screening data, we stratified by sex and student status (currently in 4-year college or not). PFI participants (both groups) completed (1) orientation and participant training (as described above), (2) four weeks of daily assessment and (3) intervention, and (4) follow-up surveys.

(3) Daily assessment. Daily assessment + feedback began on a Monday for all participants. A link to a web-based morning survey was sent at one of three times (participant choice, 5:30 am, 7am, 10am). While participants were instructed to complete the survey as early as possible, it remained available until 6pm. Text message notifications sent at noon were used to remind them their bi-weekly aggregate feedback will be less accurate if the survey is not completed (“Reminder: Complete your daily survey so that your next summary report is as accurate as possible!”). The survey format was optimized for mobile phone completion and the link was sent via SMS to maximize convenience; for security a password was required to begin.

(1) Personalized Feedback Reports. The content of the personalized feedback intervention is described briefly below.

Daily. Following each daily survey on which a participant indicated prior day drinking, optional personalized feedback was provided on how their most recent behavior (e.g., drinks last night, drinking days so far this week) compare/contrast with personal goals. Participants then chose whether to receive additional feedback in any of 7 areas: blood alcohol concentration, high risk behaviors, consequences of drinking, caloric intake, spending, how drinking compares to peers, and safe drinking strategies. All feedback reports

included feedback on drinks consumed, and then participants were asked to choose at least one additional topic for feedback (following each drinking day). Feedback drew on data collected by the Qualtrics survey at daily assessments and sometimes requiring integration with baseline data. Positive reinforcement messages for completing daily surveys and viewing feedback were displayed, and the report concluded with resources.

2- and 4-week feedback. In addition to day-level feedback, an aggregate feedback report on drinking patterns and related behaviors was delivered twice, once at the end of each 2-week period. Participants were redirected to their biweekly feedback report at the end of the daily survey/feedback on day 14 and 28. They also received a link to the biweekly feedback later that day. Once again, they had the option to view feedback across the range of topics noted above. At the end of the 2-week feedback report, participants in the intervention groups had the opportunity to update/add goals for the next 2 weeks, given what they learned thus far about their personalized behavior-outcome links. In addition to the biweekly feedback delivered via Qualtrics, participants in the intervention groups received an email with a pdf summary of their drinking over the past 2 weeks, as well as a resource list.

(3) Follow-up surveys. At the end of four weeks, participants in all three groups completed a 30-minute online survey (post-intervention). The final 30-minute follow-up took place three months after the end of intervention (four months after baseline) and assessed primary outcomes and mechanisms.

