## **ANALYSIS PLAN**

**Official Title:** Daily Personalized Drinking Feedback Delivered Via Mobile Phone

**Brief Title:** Alcohol Feedback, Reflection and Morning Evaluation

**NCT number:** NCT05509218

**Document date:** March 20, 2026

**Sample.** A total of 152 participants were enrolled, but 3 were withdrawn given determination of ineligibility. Analyses are conducted on the 149 participants who were eligible to participate. Participants in the two A-FRAME groups will be collapsed to compare receipt of intervention (regardless of incentives) to control.

**Primary outcome analyses.** The significance of between-group differences (both A-FRAME groups collapsed vs control) at the follow-ups will be obtained via ANCOVA models for continuous outcomes, adjusted for pre-test scores.

In future manuscripts, we will report both between-group effect sizes and within-group effect sizes. Additionally, we will conduct generalized hierarchical linear models to test group differences in our primary (drinks per week, frequency of heavy drinking, negative consequences; all specified as Gaussian outcomes based on their observed distributions) outcomes at 1-month and 4-months post-baseline. To represent change from baseline to 1-month and 4-months post-baseline, two time components (Time1M coded 0, 1, 0; Time4M coded 0, 0, 1, respectively) will be added at Level 1. Condition (0 = control, 1 = A-FRAME) will be added at Level 2 as a predictor of the intercept (i.e., covarying effect of group on the outcome at baseline) and both time effects (i.e., effect of group on the outcome at 1M and 4M). The effect of condition will be centered to facilitate interpretation (i.e., observation of change collapsing across groups plus any difference between groups in extent of change). Baseline social desirability will be controlled (Level 2, grand-mean centered). All intercept effects will be specified as random. Random slopes of time components will be tested and retained if significant. In reporting model results, we will rely on robust standard errors.

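### Sex and student status stratified the randomisation but are in neither planned model, so the standard errors are somewhat too wide or some precision is lost, without bias

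*Protocol*

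**What the plan says.** **Design.** Protocol, item (2) Randomization: "Using their screening data, we stratified by sex and student status (currently in 4-year college or not". On the mechanism it says that "participants were assigned using a random number table to one of these three conditions". It does not mention blocks or any other restriction within strata, and it gives no allocation ratio.

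**ANCOVA.** SAP, Primary outcome analyses: between-group differences at the follow-ups are to be "obtained via ANCOVA models for continuous outcomes, adjusted for pre-test scores". No other covariate is named.

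**Hierarchical model.** The same SAP section describes a further model with two time indicators. "Condition (0 = control, 1 = A-FRAME) will be added at Level 2 as a predictor of the intercept", and also of both time effects. The one additional covariate is described thus: "Baseline social desirability will be controlled (Level 2, grand-mean centered". The SAP does not say whether that covariate acts on the intercept only or on the time effects as well. On inference it says: "In reporting model results, we will rely on robust standard errors".

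**Sample.** "A total of 152 participants were enrolled, but 3 were withdrawn given determination of ineligibility", which leaves 149 for analysis.

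Sex and student status are in neither model as described, and the SAP does not explain why.

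**The concern.** A factor is normally used for stratification because it is expected to predict the outcome, and the analysis is then expected to reflect the design. Sex is a plausible predictor here: the guideline limits that the protocol gives participants at baseline differ for women and men.

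What is at stake depends on how assignment was done within strata.

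- **Restricted assignment (for example, blocked).** The arms are balanced on the factors by design, but a model without them leaves their variance in the residual. The reported standard error is then larger than the true one.
- **Unrestricted assignment.** Chance imbalance in sex and student status adds variability to the estimate. The reported standard error covers that variability correctly, but a smaller one was available.

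The obvious repair also has a trap. A person-level covariate entered only on the intercept of the hierarchical model does not adjust the treatment effects, which are the condition-by-time terms.

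**Working it through.** The documents give no effect size, SD, alpha, power or allocation ratio, so there is no design figure to reproduce. The size has to be shown over an assumed range.

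**Inputs**
- From the SAP: 152 − 3 = 149 analysed; linear (Gaussian) models; the two A-FRAME groups pooled against control.
- From the protocol: two binary stratification factors, so 2 × 2 = 4 strata; three arms.
- Assumed: R², the share of the outcome variance left after the pre-test score that sex and student status explain, from 0 to 0.10; two-sided alpha 0.05; 1:1:1 allocation (about 99 against 50).

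**Step 1. Analytic size for the ANCOVA**
- Reduction in SE from adjusting = 1 − √(1 − R²)
- Equivalent extra participants = 149/(1 − R²) − 149
- Type I error of the unadjusted test when strata are balanced by design = 2[1 − Φ(1.96/√(1 − R²))]

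| R² | SE reduction | Extra participants | Type I error, unadjusted, balanced strata |
|---|---|---|---|
| 0 | 0% | 0 | 0.050 |
| 0.02 | 1.0% | 3.0 | 0.048 |
| 0.05 | 2.5% | 7.8 | 0.044 |
| 0.10 | 5.1% | 16.6 | 0.039 |

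**Step 2. Simulation of the two allocation cases.** N = 149, 5,000 runs per cell, baseline correlation 0.6, each factor split 50/50. Allocation was either in permuted blocks of three within strata or simple within strata. The effect was set to give about 80% power (difference 0.389, residual SD 0.8). Each pair of rates is unadjusted / adjusted for the two factors.

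| Allocation | R² | Unadjusted: true SE / mean reported SE | Type I error | Power |
|---|---|---|---|---|
| Blocked | 0.02 | 0.1377 / 0.1392 | 0.046 / 0.048 | 0.792 / 0.796 |
| Blocked | 0.05 | 0.1362 / 0.1391 | 0.045 / 0.049 | 0.797 / 0.813 |
| Blocked | 0.10 | 0.1319 / 0.1392 | 0.038 / 0.046 | 0.800 / 0.827 |
| Simple | 0.02 | 0.1421 / 0.1397 | 0.053 / 0.053 | 0.790 / 0.795 |
| Simple | 0.05 | 0.1396 / 0.1397 | 0.051 / 0.049 | 0.787 / 0.806 |
| Simple | 0.10 | 0.1407 / 0.1398 | 0.052 / 0.050 | 0.772 / 0.818 |

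The simulation error of a type I rate is about √(0.05 × 0.95/5,000) = 0.003.

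With blocking, the estimator itself loses almost nothing (true SE at R² = 0.10: 0.1319 unadjusted, 0.1318 adjusted). Only the reported SE is too large. Without blocking, the reported SE matches the true one within simulation error, and the cost is power.

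**Step 3. Where a covariate must enter the hierarchical model.** Let x be a person-level covariate with coefficient γ on the intercept only. It adds γx to all three waves, so it cancels from each person's change from baseline. Condition acts on the intercept and both time effects. With complete data, each condition-by-time estimate is therefore the mean change under A-FRAME minus the mean change under control, with or without x. Only when x also acts on the time effects does it enter the model for change.

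A simulated complete data set (149 people, three waves, random intercept) agrees. Adding the two factors on the intercept alone left both condition-by-time estimates (−0.06789 and −0.52171) and their SE (0.22112) the same to five decimals. Entering them on the time effects as well changed the estimates and moved the SE to 0.21799. With 12% of follow-ups missing, intercept-only entry moved the estimates slightly. These values illustrate the mechanism and do not predict this trial.

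The Step 1 figures belong to the ANCOVA. In the hierarchical model the relevant quantity is how far the two factors predict change from baseline, and the documents say nothing on that.

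**The case against.** The strongest reply is that the planned analysis is already valid. Randomisation protects the comparison, the ANCOVA adjusts for the pre-test score, and chance imbalance under random assignment is sampling variation that a correct standard error covers. The pre-test score may also absorb most of what sex and student status would explain. All of this stands, and it limits the point to efficiency and calibration.

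A reader might infer more than the documents support, in four ways:

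- **That the standard errors are wrong whatever the allocation.** They are too large only if assignment was restricted within strata, and the protocol does not say that it was. The robust standard errors do not settle this, because they give no credit for stratified assignment.
- **That results are biased or false positives inflated.** Neither case does this. The unadjusted type I error is below 0.05 with blocking and about 0.05 without it.
- **That covariate adjustment is the only safeguard against imbalance.** Randomisation and the pre-test adjustment are safeguards too.
- **That the SAP places social desirability on the intercept alone.** It does not say where the term enters. This is an ambiguity to resolve, not a demonstrated error.

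A second objection is timing. The SAP reports completed enrolment and bases the Gaussian specification on observed distributions, so outcome data appear to have been seen. Changing the covariate set now adds analytic freedom. That is a good reason to label the change and keep the present analysis in view. It is not a reason to leave out factors fixed by the randomisation.

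**Conclusion.** The omission is certain: both factors were used to stratify, and neither is in either model. Its consequence is modest and depends on facts that the documents do not give. If assignment was restricted within strata, inference is conservative. If not, it is valid but less precise than it could be. At an assumed R² of 0.02 to 0.10, adjusted standard errors would be about 1% to 5% smaller. At 0.10 the simulated gain in power is about 3 points with blocking (0.800 to 0.827) and about 5 without (0.772 to 0.818). If the factors add nothing beyond the pre-test score, there is no gain. The rule on where covariates enter the hierarchical model holds exactly for complete data and approximately when few follow-ups are missing. This is worth correcting because it costs little, not because the planned result would mislead.

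**What to change.** 1. Add sex and student status as fixed covariates to every ANCOVA, beside the pre-test score.
2. In the hierarchical model, enter both on the intercept and on both time effects.
3. State where social desirability enters. If it is meant to adjust the treatment effects, put it on both time effects too.
4. State in the protocol or SAP whether assignment was blocked or otherwise restricted within strata.
5. Give the randomisation design as the reason for the added covariates, say that the change was made after outcome distributions had been examined, and report the analysis as the SAP now describes it alongside.

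**Cost.** Both variables are already held from screening. The ANCOVA loses 2 degrees of freedom: 149 − 3 = 146 before and 144 after, with complete follow-up. The hierarchical model gains 2 × 3 = 6 fixed effects for the two factors. It gains 2 more if social desirability is now on the intercept only and is extended to the time effects, making 8 in all. If the factors turn out not to be prognostic, those degrees of freedom are spent for no gain, a negligible loss at this sample size.

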## **ANALYSIS PLAN**

**Official Title:** Daily Personalized Drinking Feedback Delivered Via Mobile Phone

**Brief Title:** Alcohol Feedback, Reflection and Morning Evaluation

**NCT number:** NCT05509218

**Document date:** March 20, 2026

**Sample.** A total of 152 participants were enrolled, but 3 were withdrawn given determination of ineligibility. Analyses are conducted on the 149 participants who were eligible to participate. Participants in the two A-FRAME groups will be collapsed to compare receipt of intervention (regardless of incentives) to control.

**Primary outcome analyses.** The significance of between-group differences (both A-FRAME groups collapsed vs control) at the follow-ups will be obtained via ANCOVA models for continuous outcomes, adjusted for pre-test scores.

In future manuscripts, we will report both between-group effect sizes and within-group effect sizes. Additionally, we will conduct generalized hierarchical linear models to test group differences in our primary (drinks per week, frequency of heavy drinking, negative consequences; all specified as Gaussian outcomes based on their observed distributions) outcomes at 1-month and 4-months post-baseline. To represent change from baseline to 1-month and 4-months post-baseline, two time components (Time1M coded 0, 1, 0; Time4M coded 0, 0, 1, respectively) will be added at Level 1. Condition (0 = control, 1 = A-FRAME) will be added at Level 2 as a predictor of the intercept (i.e., covarying effect of group on the outcome at baseline) and both time effects (i.e., effect of group on the outcome at 1M and 4M). The effect of condition will be centered to facilitate interpretation (i.e., observation of change collapsing across groups plus any difference between groups in extent of change). Baseline social desirability will be controlled (Level 2, grand-mean centered). All intercept effects will be specified as random. Random slopes of time components will be tested and retained if significant. In reporting model results, we will rely on robust standard errors.

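### The primary ANCOVA has no missing-data rule, so each visit's test uses only people with that visit's score; a joint model of both follow-ups should carry it

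*SAP*

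**What the plan says.** On the analysis set, the SAP (Sample) states: "A total of 152 participants were enrolled, but 3 were withdrawn given determination of ineligibility". It continues: "Analyses are conducted on the 149 participants who were eligible to participate". It does not say when the three were found ineligible, on what information, or in which arm.

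On timing, the Protocol, section (2) Randomization, states "Randomization occurred following consent" and adds that "participants were not informed of their group until they completed the baseline survey". Stratification used screening data, so screening came before assignment.

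On the primary test, the SAP (Primary outcome analyses) compares the pooled A-FRAME groups with control at the follow-ups. Significance is to be "obtained via ANCOVA models for continuous outcomes, adjusted for pre-test scores". No imputation, missing-data assumption, missing-data sensitivity analysis or follow-up count is given. A hierarchical model of baseline, 1 month and 4 months is planned for the same primary outcomes, but as an addition meant for later manuscripts. It has a random intercept, random time slopes only if they test significant, and a free group difference at baseline.

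**The concern.** An ANCOVA of the 4-month score needs a 4-month score. Without imputation, a participant lost after 1 month leaves the 4-month test altogether, although the 1-month score says a good deal about where that person was heading. If loss at 4 months depends on 1-month drinking, and does so differently in the two arms, the people left in each arm are selected differently. Adjusting for baseline alone does not remove that. A model that also contains the 1-month score can.

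Differential loss is plausible here. A-FRAME participants were shown their drinking set against their own goals, and one of the two A-FRAME groups also had daily incentives. Nothing in the documents shows that it happened.

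The second, smaller issue is the three exclusions. If these people had already been assigned, the comparison is no longer of everyone randomised. Whether that matters depends on facts the SAP does not report.

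**Working it through.** **1. The stated analysis set.** 152 − 3 = 149, which reproduces. The excluded share is 3/152 = 1.97%.

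**2. How many the 4-month ANCOVA would use.** Retention is not in the documents, so 10% to 25% loss is an assumption: 149 × 0.90 = 134; 149 × 0.80 = 119; 149 × 0.75 = 112.

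**3. Where bias comes from.** Bias in one arm's mean = fraction missing × gap between missing and observed people. With 10% missing and a 0.5 SD gap in one arm only, it is 0.10 × 0.5 = 0.05 SD; with 20% missing, 0.20 × 0.5 = 0.10 SD. If fraction and gap are the same in both arms, the difference between arms is unaffected.

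**4. Simulation of the 4-month ANCOVA.** All settings are assumptions:
- 1:1:1 allocation, so 99 A-FRAME against 50 control after pooling
- no true effect, and scores with SD 1
- correlations of 0.6 (baseline to 1 month), 0.5 (baseline to 4 months) and 0.65 (1 to 4 months)
- baseline and 1-month scores complete
- log-odds of loss at 4 months linear in the 1-month score
- 4,000 runs per row, two-sided 5% test

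Slopes are per SD of 1-month drinking. Negative bias favours A-FRAME.

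| Loss at 4 months | Slope, A-FRAME | Slope, control | ANCOVA bias (SD) | Rejection rate |
|---|---|---|---|---|
| 20% | 1.0 | 1.0 | about 0 | 5.3% |
| 20% | 1.0 | 0.5 | −0.03 | 5.3% |
| 10% | 1.0 | 0 | −0.03 | 5.4% |
| 20% | 1.0 | 0 | −0.06 | 6.6% |
| 20–25% | 1.2 | 0 | −0.09 | 8.0% |
| 20–25% | 1.2 | −0.5 | −0.13 | 11.9% |
| 20% | 0 | 1.0 | +0.06 | 6.1% |
| 25% | −0.5 | 1.2 | +0.13 | 11.6% |

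Monte Carlo error of the bias is about 0.17/√4000 = 0.003 SD. Repeat runs moved the bias by at most about 0.01 SD.

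**5. The alternatives in the same scenarios.**
- A baseline-adjusted joint model of both follow-ups with unstructured covariance had bias within about 0.006 SD throughout, which is at the level of simulation error. Its spread was equal to or slightly below that of the ANCOVA.
- The SAP's hierarchical model with a random intercept only left bias of about 0.006 to 0.022 SD. Because it estimates change from baseline with a free baseline difference, its standard error was larger: 0.187 against 0.169, and 0.187/0.169 = 1.11. In the 20%, 1.0-against-0 case its root mean squared error was 0.188, worse than the ANCOVA's 0.180.

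**6. The three exclusions.** Under the assumed 1:1:1 split of 152, control has 152/3 = 50.7 people and pooled A-FRAME 101.3. Suppose all three were in one arm and 1 SD from its mean. The contrast then moves by 3 × 1/50.7 = 0.06 SD (control) or 3 × 1/101.3 = 0.03 SD (A-FRAME). At 2 SD these double. That is the extreme case.

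**The case against.** The strongest reply is that the documents show no loss at all. The SAP never says that people without a follow-up are dropped, and no retention figure is given. The three-wave model is already planned, and the bias rows above depend on chosen slopes. All of this is true, and it limits the claim. It does not supply the missing rule. An ANCOVA with no imputation has nothing to put in place of an absent outcome, and the three-wave model is additional to the primary test.

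Four stronger readings are tempting, and the documents do not support them.
- **That the primary test is run on completers.** A per-visit ANCOVA keeps anyone with that visit's score, including someone who missed the other visit, and whether anyone was lost is unknown.
- **That the result is biased toward benefit.** The table shows bias of either sign, or none, according to an arm contrast that is purely assumed.
- **That three randomised people were certainly dropped.** Assignment followed consent, so removal after assignment is likely if enrolled means consented, but the SAP does not say so. If ineligibility rested on facts fixed before randomisation and was judged without regard to arm, leaving these people out need not bias the comparison.
- **That daily contact made ineligibility easier to detect in the A-FRAME groups.** The Protocol has daily assessment starting on a Monday for all participants, yet elsewhere lists it only for the intervention groups. Nothing says the daily surveys collected eligibility information.

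It is also right that simply promoting the planned hierarchical model would be a poor exchange, because it loses precision and leaves some bias.

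**Conclusion.** The concern holds as a gap in the primary method. With no missing-data rule, the ANCOVA at each visit uses only people with that visit's score and ignores the 1-month data of anyone lost by 4 months. With 10% to 25% lost, the consequence runs from none (equal dependence on 1-month drinking in both arms) to roughly 0.03 to 0.13 SD in either direction (dependence clearly differing by arm). In the worst cases simulated, a nominal 5% test rejects about 12% of the time.

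These sizes rest on assumed retention, allocation, correlations and dropout slopes. The joint model's advantage also requires that loss depend only on observed scores. If it depends on unobserved 4-month drinking, neither model is protected.

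The three exclusions are the lesser part: 2.0% of those enrolled, and chiefly a matter of reporting.

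**What to change.** 1. Take the primary 1-month and 4-month group differences from a likelihood-based repeated-measures model of both follow-ups. Use baseline score as a covariate (or constrain baseline means to be equal), visit-by-group terms and unstructured covariance. Include everyone with any follow-up, in the assigned arm.
2. Keep the per-visit ANCOVA as a sensitivity analysis, with the number analysed at each visit.
3. State the missing-data assumption, and report follow-up counts by arm and visit.
4. Report the three ineligible people by assigned arm, timing of the decision and its basis. If any exclusion used information from after randomisation, add a sensitivity analysis that includes their available data.

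The cost is SAP wording and one re-run, with no loss of precision in the scenarios examined. The SAP chose Gaussian models from the observed outcome distributions, so the data have been seen. The change must therefore be disclosed as made after that point, with both sets of results shown.

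### The additional hierarchical model gives Condition a free baseline effect, so its treatment terms are differences in change: unbiased, inconsistently labelled, and less precise than the pre-test-adjusted ANCOVA

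*SAP*

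**What the plan says.** Under Primary outcome analyses, the SAP first says that the significance of between-group differences at the follow-ups "will be obtained via ANCOVA models for continuous outcomes, adjusted for pre-test scores".

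The next paragraph, which opens with plans for future manuscripts, adds a second analysis: "Additionally, we will conduct generalized hierarchical linear models to test group differences in our primary" outcomes (drinks per week, frequency of heavy drinking, negative consequences), "all specified as Gaussian outcomes based on their observed distributions". Its structure is:

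- Time: "two time components (Time1M coded 0, 1, 0; Time4M coded 0, 0, 1, respectively) will be added at Level 1". Baseline is therefore coded 0, 0 and is a row of the outcome.
- Condition is entered "as a predictor of the intercept (i.e., covarying effect of group on the outcome at baseline) and both time effects". The SAP glosses its effect on the time terms as "i.e., effect of group on the outcome at 1M and 4M". The following sentence, on centering, describes the same effect as how far the groups differ in the amount they change.
- Baseline social desirability is the only other Level 2 covariate named. The baseline value of the outcome is not a covariate in this model.

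The SAP does not say which analysis governs if the two disagree. In the Protocol's Randomization section, allocation is by random number table after consent, and "participants were not informed of their group until they completed the baseline survey".

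**The concern.** The two analyses handle a baseline difference between groups in different ways. ANCOVA removes the share that the data show to carry over to follow-up. A model with Condition on the intercept estimates the baseline difference freely and removes all of it. The SAP's gloss that this covaries the group effect at baseline could lead a reader to think the two adjustments are the same.

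Assignment was random and participants completed baseline before learning their group, so any baseline difference is chance. A free parameter for it costs precision and corrects no bias. At stake are a less precise longitudinal estimate of the primary outcomes, a coefficient with two descriptions, and two unranked results that can differ because of an avoidable modelling choice.

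**Working it through.** The documents give no power calculation, SD, correlation or allocation ratio, so there is no design figure to reproduce. The only count is 152 - 3 = 149, which is correct.

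**Inputs.** From the SAP: N = 149, the time coding, the position of Condition, and the Gaussian specification. Assumed: 1:1:1 allocation, giving about 99 (pooled A-FRAME) vs 50; complete data; equal variances over time; r between 0.3 and 0.7; two-sided alpha of 0.05.

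**Step 1: what the coefficients are.** With C for Condition and S for social desirability, the model is

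Y = b00 + b01·C + b02·S + u0 + (b10 + b11·C)·Time1M + (b20 + b21·C)·Time4M + e.

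At equal S, the group difference is b01 at baseline, b01 + b11 at 1M and b01 + b21 at 4M. So b11 and b21 are differences in change. Centering C does not alter them.

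**Step 2: numerical check.** One simulated complete data set was used (99 vs 50, r = 0.5), with a baseline difference of -0.130.

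| Estimate | 1M | 4M |
|---|---|---|
| Model as written (random intercept) | 0.6686 | 0.3873 |
| Difference in mean change | 0.6686 | 0.3873 |
| Raw follow-up difference | 0.5386 | 0.2573 |
| ANCOVA | 0.6020 | 0.3301 |
| Condition removed from intercept | 0.6182 | 0.3369 |

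The written model equals the difference in change: 0.5386 + 0.130 = 0.6686. The baseline slope implied by each adjusted estimate is its shift from the raw difference divided by 0.130. This is 1 for the written model; 0.49 (1M) and 0.56 (4M) for ANCOVA; and 0.61 at both times for the model with a common baseline mean.

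**Step 3: precision.** With variance in SD² units, the common factor is 1/99 + 1/50 = 0.0301, with square root 0.1735.

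- Var(difference in change) = 2(1 - r) × 0.0301
- Var(ANCOVA) = (1 - r²) × 0.0301
- Ratio = 2(1 - r)/(1 - r²) = 2/(1 + r)
- Equivalent N = 149 × (1 + r)/2
- Power of the written model at the effect where ANCOVA has 80%: Φ(2.80 × SE ANCOVA / SE change - 1.96)

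| r | SE change | SE ANCOVA | Variance ratio | Equivalent N | Power, written model |
|---|---|---|---|---|---|
| 0.3 | 0.2053 | 0.1655 | 1.54 | 97 | 62% |
| 0.5 | 0.1735 | 0.1503 | 1.33 | 112 | 68% |
| 0.7 | 0.1344 | 0.1239 | 1.18 | 127 | 73% |

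**Step 4: bias.** Over 4000 simulated trials with a true effect of 0.40, the mean estimates (difference in change vs ANCOVA) were 0.398 vs 0.400, 0.397 vs 0.398 and 0.400 vs 0.401 at r = 0.3, 0.5 and 0.7. Both are unbiased. Empirical SDs were 0.205 vs 0.167, 0.174 vs 0.151 and 0.135 vs 0.125, in line with the formulas.

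**Step 5: disagreement in one data set.** For a baseline imbalance D, the change estimate subtracts D and the ANCOVA subtracts about r·D, so they differ by (1 - r)·D. At D = 0.2 SD this is 0.14, 0.10 and 0.06 SD for r = 0.3, 0.5 and 0.7. One standard error of the baseline difference is 0.17 SD, so such an imbalance would be unremarkable.

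**Step 6: the remedy.** In a separate simulation at 99 vs 50, removing Condition from the intercept left the estimate unbiased, with robust interval coverage of about 95%. It cut the empirical SD from 0.211 to 0.167, 0.172 to 0.147 and 0.131 to 0.121 at r = 0.3, 0.5 and 0.7. The gain persisted with unequal correlations and with 15% of follow-up missing.

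**The case against.** Several stronger readings are tempting, and the documents do not support them.

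- **That the SAP misstates its estimand.** A reader who stops at "i.e., effect of group on the outcome at 1M and 4M" might infer this. But the SAP introduces the time components as representing change from baseline, and its next sentence correctly describes the group effect as a difference in change. The labelling is inconsistent; there is no undisclosed switch.
- **That baseline adjustment is discarded.** Baseline is an outcome row and is subtracted in full. The adjustment uses a slope of 1 instead of an estimated one.
- **That the treatment estimate is biased.** Under randomisation the two estimators have the same expectation, and the simulations agree.
- **That the main between-group test is compromised.** The ANCOVA is named first, keeps its own adjustment and does not depend on the hierarchical model.

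Three further objections stand in part. The size of the loss rests on assumed correlations and allocation, and it shrinks as r rises. The comparison with ANCOVA is derived for complete data; with dropout, a mixed model can use partial records that a visit-by-visit ANCOVA would drop, so that ranking is not established. This does not affect the comparison of the hierarchical model with and without the intercept term, since both use the same records. Finally, the phrase "all specified as Gaussian outcomes based on their observed distributions" shows that outcome data have been examined, so altering the model now is a post-data change.

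What is left is still worth correcting. The model tests all three primary outcomes at both follow-ups and sits under Primary outcome analyses, with no rule for resolving a disagreement.

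**Conclusion.** The point holds as a loss of precision and a labelling inconsistency in an additional model of the primary outcomes; it should be fixed. As written, the Condition-by-time coefficients are differences in change, with 1.18 to 1.54 times the ANCOVA variance for r from 0.7 down to 0.3. These figures assume complete data, equal variances and about 99 vs 50. The term that causes the loss protects against nothing the design leaves open, because randomisation and completion of baseline before group disclosure justify a common baseline mean. That justification also assumes that the 3 post-enrolment withdrawals for ineligibility did not depend on assigned group.

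**What to change.** 1. Remove Condition from the intercept equation so that both groups share one baseline mean, and keep Condition on Time1M and Time4M.
2. Describe those two coefficients throughout as baseline-adjusted group differences at 1M and 4M, replacing both current descriptions. They will be close to the ANCOVA but not identical: with only a random intercept, one pooled within-person correlation serves as the baseline slope at both visits.
3. State that the ANCOVA governs if the two analyses disagree.
4. Disclose that the change was made after the outcome distributions had been examined.

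If the sponsor prefers to keep the written model, the minimum is to call its coefficients differences in change everywhere and to add item 3.

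The cost is one model term, a few sentences of SAP text and a dated disclosure. No new data are needed.
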